10.0 EVALUATION DURING TREATMENT/INTERVENTION

This protocol does not require any additional evaluations after the patient is admitted for surgery other than those routinely part of clinical care for a patient undergoing a partial nephrectomy. These will include:

- ASA classification, assigned by the anesthesiologist
- Deep venous thrombosis prophylaxis per standardized pathway

- Type of anesthesia: general, epidural, combination
- Duration of anesthesia and of surgery
- Duration of warm or cold ischemia time
- Estimated blood loss
- Use of intraoperative fluids (crystalloid, colloid, blood products)
- Postoperative day 1 and postoperative day 2 serum creatinine measurement. For patients discharged before post-operative day 2, serum blood testing will be ordered as an outpatient test.
- Follow up visit serum creatinine measurements (6 weeks +/- 4 weeks and 6 months +/- 2 months)
- 6 month +/- 2 months follow up radio nuclear scintigraphy renal scan, which is a routine postoperative investigation for patients who have undergone a partial nephrectomy.
- Patients may be concurrently enrolled on protocol 89-076 for collection of tissue and blood for tissue banking.

11.0 TOXICITIES/SIDE EFFECTS

There are minimal side effects to the use of mannitol in the dosages prescribed for this study. The AHFS warnings/ precautions relate to excess amounts (>100 g of intravenous mannitol in a 24 hour period).²⁹ 12.5 g of mannitol is considered the “test dose” in adult populations when mannitol is used for other therapeutic effects. Nonetheless, concerns related to adverse effects listed are:

- Fluid/electrolyte loss: excess mannitol infusion can lead to profound diuresis with fluid and electrolyte loss; close medical supervision is required
 - The anesthesia and PACU teams routinely monitor urine output, vitals and volume status and therefore this concern is minimal.
- Nephrotoxicity: may cause renal dysfunction especially in high doses therefore caution is required in patients taking nephrotoxic agents or have pre-existing renal disease
 - Patients are excluded from participating if their eGFR identifies them as having pre-existing Stage 3b or greater chronic kidney disease. All nephrotoxic agents are closely monitored/discontinued routinely in all partial nephrectomy patients.
 - Severe clinical complications from mannitol use in the literature are exceedingly rare and only follow massive doses of mannitol, in the range of 400-900 g/day.³⁰
- Cardiovascular: may lead to chest pain, tachycardia, hypotension, hypertension, dyspnea due to congestive heart failure or overload
- Respiratory: Pulmonary edema
- Central Nervous System: Pyrexia, headache, confusion, vertigo
- Dermatological: Urticaria
- Gastrointestinal: Nausea, emesis, xerostomia

Surgical complications will be assessed prospectively and retrospectively reviewed using the institutional standard for complications reporting for all surgical patients as followed by the Department of Surgery. Standardized graded complications and adverse events at MSKCC utilize the five point modified Clavien system. Grade I include complications requiring

monitoring but no intervention, Grade II requires bedside or medical treatment; grade III constitutes adverse events require surgical or procedural intervention with return to normal functioning; grade IV includes disabling, life-threatening complications with resulting functional loss and grade V is the death of the patient. This is a modification of the Clavien system for reporting complications with defined, categorized, and classified events that will be segregated into time periods of ≤ 30 days, 31 - 90 days and > 90 days after surgery and includes medication related complications following NCI CTCAE version 3 guidelines.³¹

12.0 CRITERIA FOR THERAPEUTIC RESPONSE/OUTCOME ASSESSMENT

As an intent-to-treat study, patients will be evaluated for the primary endpoint if they are registered on study, brought to the operating room for surgery, and begin anesthesia for the procedure. Because the role of mannitol as a protective agent in regard to kidney function is not entirely clear and its mechanism of action may be mediated through its effects on the contralateral kidney, all patients will be evaluated for the primary endpoint even if the ipsilateral kidney is not clamped during the procedure. If the surgery is aborted for any reason before attempted excision of the mass or if intravenous infusion fails for any reason the patient will be dropped from the study and replaced. Based on past experience these issues are rare events.

Estimated glomerular filtration rate (eGFR) will be estimated according to the CKD-EPI formula.

Perioperative complications are defined as any complication graded in the MSKCC grading system occurring during the intraoperative and postoperative period up to 30 days.

Immediate perioperative morbidity is defined as any complication graded in the MSKCC grading system occurring during the initial hospital stay.

The intraoperative period is defined as the period from anesthesia induction to final skin closure.

The postoperative period is defined as the period from final skin closure to the study endpoint at 6 months \pm 2 months.

Renal hypothermia will be defined as induced cooling of the kidney by externally applied ice-slush or cold crystalloid infusion via catheter of the renal pelvis or intravascularly.

Warm ischemia will be defined as no kidney cooling during renal artery occlusion.

Ischemia time will be defined as the time elapsed from renal artery occlusion by a vascular clamp to removal of the vascular clamp. Re-clamping of the vessels will be recorded as an event and total duration of ischemia recorded as the sum duration of occlusion.

Blood loss is defined as the estimate accounted from the suction device and absorptive sponges during the surgical procedure, and will be noted in the anesthesia record per institutional standard.

Intraoperative complications are defined as any complications related to either surgical or clinical aspects during the procedure, as described by the surgeon and covered by the institutional guidelines.

Any patient who does not undergo renal ischemia by vascular clamping will during their procedure will be recorded as a zero ischemia time.

13.0 CRITERIA FOR REMOVAL FROM STUDY

Patients will be withdrawn from the study if they express a desire to do so, if it is determined to be in the patient's best interest to do so, or if they do not undergo initiation of their surgical procedure as stipulated in section 12.0. Patients who are not evaluable for the study primary endpoint by failure to obtain data for the primary endpoint will be excluded from the analysis and replaced.

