2.0 OBJECTIVES AND SCIENTIFIC AIMS

Primary endpoints:

- Difference in eGFR at 6 months after surgery.

Secondary endpoints:

- Difference in eGFR at 6 weeks after surgery.
- Difference in radionuclear scintigraphy renal scan at 6 months postoperatively.
- Difference in rate of grade 3-5 complications within 30 days of surgery.
- Difference in estimated blood loss.
- Difference in ischemia time.

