14.0 BIOSTATISTICS

14.1 Primary Aim

The primary aim is to establish the difference in eGFR 6 months after surgery between the mannitol group and the placebo group. The difference will be assessed with an ANCOVA model with eGFR 6 months after surgery (+/- 2 months) as the outcome and treatment group, surgical technique, and preoperative eGFR as covariates. We will report a two-tailed p-value and a 95% confidence interval for the difference between groups. If a patient does not have an eGFR measurement between 5-7 months after surgery and has both a measurement between 3-5 months and 7-12 months after surgery, then the 6 month eGFR measurement will be linearly interpolated.

Based on historical data, patients not receiving mannitol have a mean eGFR of 60 cc/min/1.73m² 6 months after surgery. The observed correlation between the preoperative eGFR and eGFR 6 months was 0.6. The standard deviation is 14.4. Using bootstrap methods, the 75th percentile of the standard deviation was estimated to be 14.9. This inflated standard deviation was used in the sample size calculation. To detect the minimal clinical significant difference of 6 units of eGFR, a trial with 90% power and 5% alpha requires 83 patients per treatment arm. Because of the loss of power in the interim analysis, a total of 88 patients are required per treatment arm. The trial will accrue until it is anticipated that 88 patients per treatment arm will have evaluable eGFRs at 6 months. We expect that, due to drop out, this will involve accruing approximately 105 patients per treatment arm. Sensitivity analyses will be performed to assess the effect of patient withdrawal on the primary analysis.

We expect to reach our target sample size within 2 years, given that nearly 200 patients per year are eligible to enroll. We expect to enroll 8 patients per month to reach accrual in 2 years.

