14.2 Secondary Aims

An ANCOVA model will be used to compare the difference in eGFR between treatment groups at 6 weeks (+/- 4 weeks) after surgery with postoperative eGFR as the outcome, and treatment group, surgical technique, and preoperative eGFR as covariates.

We will also use the ANCOVA on the absolute level of eGFR because this has the greatest statistical power. However, the estimate produced by ANCOVA – a mean difference in eGFR levels – is of incomplete clinical interpretability. We will therefore present estimates in two other ways for the purposes of illustrating the results in clinical terms. We will first give percentage change separately by group, along with a difference between groups. We will also report the percentage of patients in each treatment group that have postoperative eGFR less than 60 ml/min/1.73 m², as this is generally considered to represent a clinical level of kidney dysfunction.

ANCOVA will be used to compare 6 month (+/- 2 months) postoperative radionuclear scintigraphy renal scan with treatment group, baseline postoperative radionuclear scintigraphy renal scan, and randomization stratum as covariates. ANCOVA will also be used to compare estimated blood loss and ischemia time with treatment group and randomization stratum as covariates.

Multivariable logistic regression will be used to assess the difference in the rate of grade 3-5 complications between treatment groups. The multivariable model will include treatment group and randomization stratum as covariates.

We will report a two-tailed p-value and a 95% confidence interval for the difference between groups for all secondary outcomes. Summary statistics will be calculated by group for age, sex, race, BMI, serum hemoglobin, serum albumin, ASA, and Karnofsky Performance Scale.

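### As worded, the removal and replacement rules in Sections 12.0 and 13.0 can take deaths and other severe events out of the 30-day grade 3-5 comparison, and Section 14.2 names no population that keeps them in

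*Combined protocol and SAP*

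**What the plan says.** Section 2.0 sets the primary endpoint as "Difference in eGFR at 6 months after surgery" and lists among the secondary endpoints "Difference in rate of grade 3-5 complications within 30 days of surgery". Section 11.0 defines the grading scale, on which "grade V is the death of the patient".

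Two rules decide who leaves:

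- Section 13.0: patients not evaluable for the primary endpoint because of "failure to obtain data for the primary endpoint will be excluded from the analysis and replaced".
- Section 12.0: if surgery is aborted before excision is attempted, or "if intravenous infusion fails for any reason the patient will be dropped from the study and replaced". The plan expects such cases to be rare.

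Section 12.0 opens with a broader principle: "As an intent-to-treat study, patients will be evaluated for the primary endpoint if they are registered on study", provided that they also reach the operating room and begin anaesthesia. That sentence covers the primary endpoint only. The same section counts perioperative complications over the intraoperative period and up to 30 days after it, and starts the intraoperative period at anaesthesia induction.

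For the complication analysis, Section 14.2 specifies a logistic regression: "The multivariable model will include treatment group and randomization stratum as covariates". It states no analysis population. The sensitivity analyses in Section 14.1 concern withdrawal and the primary analysis only.

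**The concern.** Whether a patient had a grade 3-5 complication within 30 days can be established for nearly everyone operated on. It does not require a blood test six months later, a completed infusion or a completed resection. The exclusion and replacement rules depend on exactly those later or downstream facts, and neither rule is confined to the eGFR analysis.

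A patient who dies in the first 30 days has the worst outcome on the scale and can never supply the primary endpoint. A severe event after induction that leads to the operation being abandoned counts as a complication by definition, yet it also triggers removal from the study. In both cases the event itself causes the exclusion. The comparison is of few events, in a protocol that itself cites theoretical arguments that mannitol may do harm (Section 17.0), so one or two omissions could change how it reads.

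How the primary eGFR analysis handles missing values is a separate matter.

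**Working it through.** **1. The plan's own figures.** Inputs from Section 14.1: difference 6, SD 14.9, correlation 0.6, two-sided 5% alpha, 90% power; 1:1 allocation from Section 4.1.

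n per arm = 2 × [SD × √(1 − r²) × (z₀.₉₇₅ + z₀.₉₀) / difference]² = 2 × [14.9 × 0.8 × (1.960 + 1.282) / 6]² = 82.94 with unrounded quantiles, so 83. This matches the plan.

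Taking the plan's 88 evaluable per arm after the interim adjustment as given, 88 / (1 − 0.16) = 104.8, so 105. This also matches. The implied loss is (105 − 88) / 105 = 17/105 = 16.2% per arm, or 34 of 210 overall.

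**2. A patient who dies within 30 days.** The primary analysis is an "ANCOVA model with eGFR 6 months after surgery (+/- 2 months) as the outcome", so the earliest usable value is at four months. The interpolation rule in Section 14.1 needs measurements at both 3-5 and 7-12 months. Neither route can yield a value, so the patient meets the Section 13.0 condition. The death is grade V and falls inside the complication window. Nothing in Sections 12.0, 13.0 or 14.2 returns the patient to the complication analysis.

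**3. A severe event after induction that aborts surgery before excision.** Anaesthesia has begun, so the patient is in the set that Section 12.0 first describes. The event is intraoperative, so it is a complication by the same section's definition. The later sentence in that section then drops the patient from the study and replaces them. A failed infusion follows the same path. This step does not depend on how Section 13.0 is read.

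**4. What losing deaths does to a rate.** With x events in n patients, removing d deaths changes x/n to (x − d)/(n − d), which is lower whenever x < n. The documents give no rates, so these counts are assumed: 105 patients in an arm, four of them with non-fatal grade 3-4 events.

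- 1 death: 5/105 = 4.8% becomes 4/104 = 3.8%
- 2 deaths: 6/105 = 5.7% becomes 4/103 = 3.9%
- 3 deaths: 7/105 = 6.7% becomes 4/102 = 3.9%

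**5. What losing other patients does.** Take four non-fatal events, no deaths and 17 patients lost. The full rate is 4/105 = 3.8%. If none of the 17 had an event, the analysed rate is 4/88 = 4.5%. If two of the 17 did, it is 2/88 = 2.3%. The direction depends on who is lost.

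**6. Whether any death is likely.** At an assumed 30-day mortality p, the chance of at least one death among 210 patients is 1 − (1 − p)²¹⁰:

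- p = 0.2%: 34% (0.42 deaths expected)
- p = 0.5%: 65% (1.05 expected)
- p = 1%: 88% (2.1 expected)
- p = 2%: 99% (4.2 expected)

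**The case against.** The best defence is that Section 13.0 was meant for the primary ANCOVA alone. Its sentence is about evaluability for the primary endpoint, it speaks of a single analysis, and replacement serves the target of 88 evaluable eGFR values per arm. Section 13.0 also lists separately who is withdrawn from the study, and a missing eGFR is not on that list. Section 14.2 does not restrict the complication model to patients with an eGFR. This reading is reasonable, and the authors may have intended it. But the text does not say so, and it leaves Section 12.0 untouched, where the drop is from the study and not from one analysis.

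Several stronger inferences are tempting, and the documents do not support them:

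- *Every 30-day death is certain to be lost.* That follows only from the literal reading of Section 13.0.
- *16% of the complication data will be missing.* Section 14.1 does not break down its drop-out allowance. Patients who withdraw or never start surgery have no operative outcome to lose.
- *The complication rate is biased downward overall, or differently by arm.* Only the effect of losing deaths has a known direction. A difference between arms would require mannitol to influence the events that trigger removal, which is not known.
- *This is the trial's only safety comparison.* The eGFR comparisons at 6 weeks and 6 months also bear on nephrotoxicity, a risk listed in Section 11.0. Serious adverse events are reported to the IRB within 5 calendar days (Section 17.2), so a death would be recorded. What is open is whether it enters the between-arm comparison.
- *Patients with a drug reaction are explicitly removed.* Section 12.0 does not define a failed infusion or mention reactions. Its wording is wide enough to include an infusion stopped for one, but that is an inference.

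**Conclusion.** The point holds in a limited form. As worded, the rules in Sections 12.0 and 13.0 can remove 30-day deaths, and severe events that abort surgery or stop the infusion, from the grade 3-5 comparison. No sentence keeps them in. The part about deaths with no 6-month eGFR rests on reading Section 13.0 literally. The part about aborted surgery and failed infusion holds on either reading of Section 13.0.

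At the plan's expected drop-out, at most about 17 of 105 accrued patients per arm (16%) are affected. The size of any bias cannot be derived, because the documents give neither complication nor mortality rates; the counts and mortality range used above are assumptions for illustration. The endpoint is secondary, and the sample size and primary analysis are unaffected. The repair should still be made before analysis, because it is cheap and the patients at issue include those with the worst outcomes.

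**What to change.** In Sections 12.0 and 13.0, state that the exclusion and replacement rules apply only to the primary eGFR analysis.

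In Section 14.2, state that 30-day grade 3-5 complications are analysed by randomised arm in all randomised patients who began anaesthesia, the set with which Section 12.0 already starts. Inclusion should not depend on whether the infusion was completed, surgery was aborted, a 6-month eGFR exists or the patient was replaced. Deaths within 30 days count as grade 5. Patients who withdraw consent contribute data up to withdrawal.

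The cost is about two sentences. Section 11.0 already has complications assessed under the institutional standard for all surgical patients, so no new data collection is needed. The one drawback is that the complication denominator will differ from that of the primary analysis, so reports should show both.

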14.0 BIOSTATISTICS

14.1 Primary Aim

The primary aim is to establish the difference in eGFR 6 months after surgery between the mannitol group and the placebo group. The difference will be assessed with an ANCOVA model with eGFR 6 months after surgery (+/- 2 months) as the outcome and treatment group, surgical technique, and preoperative eGFR as covariates. We will report a two-tailed p-value and a 95% confidence interval for the difference between groups. If a patient does not have an eGFR measurement between 5-7 months after surgery and has both a measurement between 3-5 months and 7-12 months after surgery, then the 6 month eGFR measurement will be linearly interpolated.

Based on historical data, patients not receiving mannitol have a mean eGFR of 60 cc/min/1.73m² 6 months after surgery. The observed correlation between the preoperative eGFR and eGFR 6 months was 0.6. The standard deviation is 14.4. Using bootstrap methods, the 75th percentile of the standard deviation was estimated to be 14.9. This inflated standard deviation was used in the sample size calculation. To detect the minimal clinical significant difference of 6 units of eGFR, a trial with 90% power and 5% alpha requires 83 patients per treatment arm. Because of the loss of power in the interim analysis, a total of 88 patients are required per treatment arm. The trial will accrue until it is anticipated that 88 patients per treatment arm will have evaluable eGFRs at 6 months. We expect that, due to drop out, this will involve accruing approximately 105 patients per treatment arm. Sensitivity analyses will be performed to assess the effect of patient withdrawal on the primary analysis.

We expect to reach our target sample size within 2 years, given that nearly 200 patients per year are eligible to enroll. We expect to enroll 8 patients per month to reach accrual in 2 years.

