Overall renal function appears to transiently decrease following nephron sparing surgery in a manner which suggests delayed recovery. As demonstrated in Figure 1, the profile of renal function, as assessed by eGFR, appears comparable for patients managed with and without mannitol based on retrospective data. Overall, the recovery of renal function was very similar in both groups ($p=0.8$ for effect of mannitol from GEE model). The predicted eGFR for a typical patient 2 months after surgery was 62 ml/min/1.73m² both for those given and not given mannitol; at 6 months the respective predicted GFR measurements were 63 and 64 ml/min/1.73m². It is notable that the mannitol group had a lower nadir and recovery of eGFR than the group who did not receive mannitol. In evaluating the open surgical experience in over 850 open partial procedures 34 did not receive mannitol, many of who did not require renal ischemia, limiting our evaluation of this cohort.

[figure not shown]

Figure 1. Population-averaged changes in GFR ($\text{mL}/\text{min}/1.73\text{m}^2$) after partial nephrectomy for patients given mannitol (grey line) and not given mannitol (black line), adjusted for differences in preoperative GFR, age, gender, ASA score, estimated blood loss, and ischemia time. Dashed lines indicate 95% confidence intervals. The histogram shows the number of GFR measurements over time, excluding postoperative measurements taken within two days of surgery that were recorded for all patients.

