8.0 PRETREATMENT EVALUATION

This protocol does not require any additional pretreatment evaluations other than those which are part of current clinical care standards for a patient undergoing a partial nephrectomy at MSKCC. These include:

- Baseline radionuclear scintigraphy renal scan within 6 months of surgery
- Routine history and physical examination to include documentation of any comorbidities, medications (including complementary and alternative medications), family history, social history (alcohol and tobacco usage), height, body weight, Karnofsky performance status within 30 days of surgery
- Abdominal and pelvic CT scan and/or renal ultrasound within 3 months of surgery
- Chest X-ray or Chest CT scan within 3 months of surgery
- Preoperative laboratory investigations: CBC, basic chemistry panel, urinalysis (dipstick, microalbumin, creatinine, microscopic evaluation if indicated), urine culture if indicated within 30 days of surgery
- Baseline creatinine values will be converted to eGFR using the CKD-EPI equation.
 - This value will be recorded from the MSKCC pre-surgical testing blood work mandatory for all patients undergoing surgery at MSKCC

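### The 6-month and 6-week eGFR models could also adjust for age and the baseline renal scan, which the trial already has: a cheap, optional gain in precision of unknown and probably modest size

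*Combined protocol and SAP*

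**What the plan says.** Section 14.1 defines the primary model as an ANCOVA with 6-month eGFR "as the outcome and treatment group, surgical technique, and preoperative eGFR as covariates". Section 14.2 repeats these covariates for the 6-week comparison and explains that ANCOVA on the eGFR level was chosen for its power.

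The documents treat other baseline information as follows:

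- **Age** is an eligibility criterion (6.1), but in the analysis it appears only among the descriptive summaries (14.2).
- **The renal scan** is listed in Section 8.0: "Baseline radionuclear scintigraphy renal scan within 6 months of surgery". Section 14.2 uses a baseline scan as a covariate for the scan endpoint only. The text there calls it both baseline and postoperative; I read it as the scan of Section 8.0. The operated kidney's share of function is not named anywhere.
- **Tumour size** is not named as a data item. Section 8.0 lists only the imaging it could be read from: "Abdominal and pelvic CT scan and/or renal ultrasound within 3 months of surgery".

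The sponsor's retrospective model (Section 3.0, Figure 1) was "adjusted for differences in preoperative GFR, age, gender, ASA score, estimated blood loss, and ischemia time". Section 15.2 stratifies on eGFR category and surgical approach, so both stratification factors are represented in the primary model.

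**The concern.** Total eGFR after partial nephrectomy is the sum of two kidneys, and only one is operated on. A single preoperative total cannot show how much function lies on the operated side. Solitary kidneys are not excluded in 6.1 or 6.2. The baseline scan is the obvious source of that information, yet the eGFR models do not use it.

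The planning correlation of 0.6 leaves 1 − 0.36 = 64% of the outcome variance unexplained by preoperative eGFR. In a randomised comparison, prespecified adjustment for prognostic values fixed before the infusion reduces that residual without bias.

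What is at stake is the width of the confidence interval. Section 3.0 reports predicted 6-month values of 63 and 64 with p = 0.8. If the trial finds something similar, its message will rest on which differences the interval excludes.

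**Working it through.** **Inputs from 14.1.** Difference 6 units; "The observed correlation between the preoperative eGFR and eGFR 6 months was 0.6"; "the 75th percentile of the standard deviation was estimated to be 14.9"; "a trial with 90% power and 5% alpha requires 83 patients per treatment arm"; 88 evaluable per arm after the interim allowance. Section 4.1 gives a final significance level of 0.049.

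**Step 1: reproduce the plan's figure.**
- Residual SD = 14.9 × √(1 − 0.6²) = 14.9 × 0.8 = 11.92.
- n per arm = 2 × [11.92 × (1.960 + 1.282) / 6]² = 82.9, so 83. This matches.
- The stated power therefore needs no covariate beyond preoperative eGFR.

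**Step 2: precision of the current model at 88 per arm.**
- SE = 11.92 × √(2/88) = 1.797.
- 95% half-width = 1.96 × 1.797 = 3.52.
- Power for 6 units at the 0.049 level = Φ(6/1.797 − 1.969) = 91.5%.

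**Step 3: cost of extra terms.** With 176 patients, the variance of the treatment estimate is inflated on average by chance correlation between treatment and the added covariates. Going from two covariates to five, the factor is (176 − 3 − 2)/(176 − 3 − 5) = 171/168 = 1.018, about 1.8%.

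**Step 4: net effect.** Let x be the share of residual variance that the three added terms explain. The documents give no value for x, so the range is an assumption.

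Net SE = 1.797 × √[(1 − x) × 171/168]

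| x | Net SE | 95% half-width | Power for 6 units | Equivalent n per arm |
|---|---|---|---|---|
| Current model | 1.797 | 3.52 | 91.5% | 88 |
| 2% | 1.795 | 3.52 | 91.5% | 88 |
| 5% | 1.767 | 3.46 | 92.3% | 91 |
| 10% | 1.720 | 3.37 | 93.6% | 96 |
| 15% | 1.671 | 3.28 | 94.7% | 102 |

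Equivalent n is 88 / [(1 − x) × 171/168].

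**Step 5: break-even and worst case.**
- (1 − x) × 171/168 = 1 gives x = 3/171 = 1.8%. Below this the extra terms lose a little.
- If they explain nothing, the half-width becomes 3.52 × √1.018 = 3.55.
- Two missing-value indicators make five added terms. The factor is then 171/166 = 1.030 and break-even is 5/171 = 2.9%.

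These figures apply to 6 months only. The documents give no SD or correlation for the 6-week outcome.

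**The case against.** The strongest reply is that nothing here is broken, and that part stands in full. The primary model contains the baseline value of the outcome and represents both stratification factors. Randomisation protects its validity, its interval already allows for chance imbalance, and the sample size reproduces without further covariates. A reader might infer from the omission that the analysis is biased or underpowered; the documents support neither.

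Two other tempting readings also fail. The first is that the missing predictors are collected on every patient. Only age is named as an analysis variable. Operated-kidney share and tumour size would have to be derived from a scan and imaging done as routine care, so completeness is not assured, and CT and ultrasound may measure size differently. The second is that the precision is free. Each term costs a little, and complete-case handling of a partly missing covariate could cancel the gain.

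It can also be said that the gain has no anchor in the documents, which is true. Age is the least certain: Section 3.0 specifies its CKD-EPI index patient by age, race and sex, which suggests that age already enters both eGFR values. Nor does the retrospective model show prognostic strength, since it adjusted a non-randomised comparison of groups that differed at baseline.

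Finally, an estimate near zero with a half-width of 3.52 already excludes 6 units. At x = 10% the improvement is 3.52 − 3.37 = 0.15 units, which is unlikely to change the conclusion.

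These points reduce the recommendation to an option. They do not remove it: the sponsor's own reason for choosing ANCOVA applies equally to further prognostic baseline covariates, and the worst case in Step 5 is small.

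**Conclusion.** The point holds as an optional efficiency improvement. The 6-month and 6-week eGFR models are valid, and the primary comparison has about 91.5% power for 6 units at 88 per arm. They do not use age or the baseline scan, although the trial has both before surgery.

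For an assumed added R² of 5% to 15%, the net benefit is a half-width 0.06 to 0.24 eGFR units narrower (3.52 to between 3.46 and 3.28), worth about 3 to 14 evaluable patients per arm. At about 2% or less there is none. This rests on three assumptions: the planning SD of 14.9 and correlation of 0.6 hold, three terms are added, and no patient is lost to a missing covariate. The value of x cannot be settled from the documents. The sponsor could estimate the contribution of age from its retrospective cohort, and that of the scan if scan data are available there.

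**What to change.** Before unblinding, amend the eGFR models in 14.1 and 14.2 as follows:

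- Keep treatment, surgical technique and continuous preoperative eGFR.
- Add age and the operated kidney's share of function from the scan taken before surgery.
- Add tumour size only if it is recorded from imaging before surgery.
- Fill a missing baseline covariate with the overall mean plus a missing indicator, so that no patient is dropped.
- Do not adjust for ischemia time or blood loss. Both arise after the infusion and are secondary endpoints in Section 2.0.
- Keep the currently stated model as a sensitivity analysis.

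The cost is a sentence or two in each section, abstraction of the scan share (and of tumour size if used) from routine records, and three to five degrees of freedom. No extra patient assessments are needed and the sample size does not change.
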